4.2.2.5 Sensitivity Analyses of the Secondary Endpoint

No sensitivity analyses will be performed for secondary endpoints (PK and PD).

4.2.2.6 Subgroup Analyses

No subgroup analyses will be performed for secondary endpoints (PK and PD).

4.2.3 Other Endpoints – Exploratory

4.2.3.1 Definition

The exploratory endpoints are:

- SARS-CoV-2 RT-PCR-positive symptomatic illness (including COVID-19 hospitalization or death)
- Post-treatment response for SARS-CoV-2 nucleocapsid antibodies
- SARS-CoV-2 RT-PCR-positive severe or critical symptomatic illness, defined for SARS-CoV-2 RT-PCR-positive symptomatic illness and met the severe criteria, and COVID-19 deaths
- PK of AZD7442 in Nasal Fluid (NLF)

Similar to serum PK samples, NLF samples will be collected following the same schedule as for the serum samples. NLF raw concentrations of AZD7442 is calculated as the sum of raw NLF concentrations for AZD8895 and AZD1061. For a subset of 20 participants, samples will be additionally collected at Day 3 and Day 11. Adjusted (by ratio of serum and NLF urea) NLF concentrations as well as ratio of serum PK concentration and NLF PK concentration (i.e., Serum:NLF partition ratio) will be calculated using the following formula:

$$\text{Adjusted NLF concentration} = \text{Raw NLF concentration [ng/mL]} * (1000 * \text{Serum Urea [mmol/L]} / (\text{NLF Urea [\mu mol/L]}))$$

$$\text{Serum:NLF Partition Ratio (\%)} = 100\% * (0.001 * \text{Adjusted NLF concentration [ng/mL]} / (\text{Serum concentration [\mu g/mL]}))$$

When Raw NLF concentration < LLOQ for either AZD8895 or AZD1061, replace it with LLOQ for the calculation.

4.2.3.2 Derivations

Categorical and continuous endpoints are shown in Section 4.2.3.1.

4.2.3.3 Handling of Dropouts and Missing Data

Unless otherwise specified, missing data will not be imputed. NLF PK analyses will be based on participants with data available. However, the following imputation methods will be used for descriptive analyses of NLF PK.

NLF PK data

Individual concentrations that are <LLOQ will be reported as <LLOQ in the listings for AZD8895 and AZD1061. Value of LLOQ will be used for both raw and adjusted AZD8895 and AZD1061 concentrations in summaries of AZD8895 and AZD1061 concentrations. AZD7442 concentration is sum of AZD8895 and AZD1061 concentrations, calculated after setting <LLOQ to LLOQ. Adjusted AZD7442 concentration is same as raw AZD7442 concentration in such cases.

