3.2 Analysis Populations

Table 2: Populations for Analysis

Population/Analysis	Description
Enrolled	All participants who sign the ICF.
Full analysis set	All randomized participants who receive at least one dose of IMP. Participants will be assigned to their randomized treatment according to the intent-to-treat principle.
Safety analysis set	All participants who have received at least one dose of IMP. Participants will be assigned in this analysis set by the arm of treatment they actually received.
PK analysis set	All participants in the safety analysis set who received AZD7442 ¹ and who had at least one quantifiable serum PK observation post dose will be included in the PK analysis dataset. Participants will be assigned in this analysis set by the arm of treatment they actually received.
NLF PK analysis set	All participants in the safety analysis set who received AZD7442 ¹ and who had at least one quantifiable adjusted nasal lining fluid PK observation post dose will be included in the NLF PK analysis dataset. Participants will be assigned in this analysis set by the arm of treatment they actually received.
ADA evaluable analysis set	All participants in the safety analysis set who have a non-missing baseline AZD7442 ADA result and at least one non-missing post-baseline AZD7442 ADA result. This includes 2 separate evaluable analysis sets for AZD8895 and AZD1061. AZD7442 evaluable analysis set contains participants who are either AZD8895 evaluable or AZD1061 evaluable. Participants will be assigned in this analysis set by the arm of treatment they actually received.
nAb evaluable analysis set (Pseudovirus)	All participants in the safety analysis set who received AZD7442 ¹ , and who had at least one quantifiable serum observation (pseudovirus) post dose. Participants will be assigned in this analysis set by the arm of treatment they actually received.

Population/Analysis	Description
nAb evaluable analysis set (Authentic Virus)	All participants in the safety analysis set who received AZD7442 ¹ , and who had at least one quantifiable serum observation (authentic virus) post dose. Participants will be assigned in this analysis set by the arm of treatment they actually received.

Abbreviations: ICF, informed consent form; COVID-19, coronavirus disease 2019; IMP, investigational medicinal product.

¹As per participant-level exclusions from the analyses identified in the most recent version of the PDMP.

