3.3 General Considerations

Categorical variables will be summarized using frequency and percentages, where the denominator for calculation is the underlying analysis set population, unless otherwise stated. A row denoted as “Missing” will be included in the count tabulations where necessary to account for missing values. Summaries will be provided by treatment and visit when applicable.

Continuous variables may be summarized with descriptive statistics of number of participants with available data (n), mean, standard deviation (SD), median, the first quartile (Q1), third quartile (Q3), minimum and maximum. Summaries will be provided by treatment and visit when applicable.

For concentration data and log-transformed data, descriptive statistics (i.e., n and n < lower limit of quantification (LLOQ) [number of participants with available result and number of participants with results below the limit of quantification], geometric mean, geometric SD, arithmetic mean, SD, co-efficient of variation, median, min and max) will be presented by treatment group and visit, when applicable.

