4.2.3.4.4 PK of AZD7442 in Nasal Fluid

NLF PK analysis will be based on actual treatment in the NLF PK Analysis Set. Same record exclusion criteria as explained in previous section 4.2.2.4.1 will be applied.

Individual AZD7442 (AZD8895 and AZD1061) adjusted NLF concentrations data and serum to NLF partition ratio will be listed and tabulated by mAb component, along with descriptive statistics for the NLF PK analysis set for each treatment group.

Figures of adjusted NLF concentrations and serum to NLF partition ratio by mAb component and treatment group will also be presented. The figures will include the subset of 20 participants with additional NLF PK measurements.

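### SAP 4.2.3.1 and 4.2.3.3 give conflicting adjusted values for a nasal lining fluid result below LLOQ, so the concentration summaries and the partition ratio may rest on different values

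*SAP*

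**What the plan says.** SAP 4.2.3.1 (Definition) introduces two derived NLF quantities: "Adjusted (by ratio of serum and NLF urea) NLF concentrations as well as ratio of serum PK concentration and NLF PK concentration". The adjusted concentration is the raw concentration times 1000 x serum urea (mmol/L) / NLF urea (µmol/L). The partition ratio has that adjusted concentration in its numerator and the serum concentration in its denominator. Directly below both formulas comes the first rule for censored values: "When Raw NLF concentration < LLOQ for either AZD8895 or AZD1061, replace it with LLOQ for the calculation".

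SAP 4.2.3.3 (Handling of Dropouts and Missing Data) gives a second rule, for descriptive NLF analyses: "Value of LLOQ will be used for both raw and adjusted AZD8895 and AZD1061 concentrations in summaries of AZD8895 and AZD1061 concentrations". It forms AZD7442 as the sum of the two antibodies after substitution, and adds: "Adjusted AZD7442 concentration is same as raw AZD7442 concentration in such cases". It does not mention the partition ratio.

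SAP 4.2.3.4.4 uses both quantities: "adjusted NLF concentrations data and serum to NLF partition ratio will be listed and tabulated by mAb component". It also plans plots of both: "Figures of adjusted NLF concentrations and serum to NLF partition ratio by mAb component and treatment group will also be presented". For concentration data, SAP 3.3 requires, besides n and the number below LLOQ, "geometric mean, geometric SD, arithmetic mean, SD, co-efficient of variation, median, min and max) will be presented by treatment group and visit".

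**The concern.** The two sections assign different adjusted values to the same censored component, and no sentence says which prevails. One applies the urea correction to the substituted LLOQ; the other does not. Section 4.2.3.3 confines its component rule to concentration summaries, so the partition ratio is left to the rule in 4.2.3.1. Two outputs that appear together by antibody could therefore be built on different numbers for the same sample, and two programmers could produce different tables from the same SAP.

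There is a further effect if 4.2.3.3 is followed literally. Quantifiable samples enter the geometric and arithmetic means on the urea-adjusted scale, while censored samples enter on the raw scale. A summary of that mixture is hard to interpret, and increasingly so as the censored share grows.

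**Working it through.** **Inputs.** The formulas and both substitution rules come from SAP 4.2.3.1 and 4.2.3.3. The documents give no LLOQ, no urea values and no share of samples below LLOQ. The plan states no figure to reproduce.

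**Step 1: units.** D = 1000 x serum urea [mmol/L] / NLF urea [µmol/L]. The 1000 converts mmol to µmol, so D is a dimensionless dilution factor specific to the sample.

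**Step 2: one component below LLOQ.**
- Under 4.2.3.1: raw := LLOQ, so adjusted = LLOQ x D.
- Under 4.2.3.3: adjusted = LLOQ.
- Quotient = D. The rules agree only when D = 1. The 4.2.3.3 value is the lower one if D > 1 and the higher one if D < 1.

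**Step 3: partition ratio.** The ratio is 100% x 0.001 x adjusted / serum. Its value from 4.2.3.1, divided by the value obtained by inserting the 4.2.3.3 figure, is again D. Assumed example with LLOQ = 1 ng/mL, serum = 10 µg/mL and D = 10:
- 4.2.3.1: 100 x 0.001 x 10 / 10 = 0.10%.
- 4.2.3.3 value carried in: 100 x 0.001 x 1 / 10 = 0.01%.

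**Step 4: step in scale under 4.2.3.3.** A raw result exactly at LLOQ is summarized as LLOQ x D. One just below it is summarized as LLOQ.

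**Step 5: geometric mean at a visit.** Samples at or above LLOQ are identical under both rules. With n samples, of which a share f is below LLOQ:

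log GM(4.2.3.1) − log GM(4.2.3.3) = (1/n) x sum of log D over below-LLOQ samples = f x log G,

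so the ratio of geometric means is G^f. Here G is the geometric mean of D among the below-LLOQ samples; D need not be the same in each.

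| Assumed G | f = 10% | f = 25% | f = 50% |
|---|---|---|---|
| 0.5 | 0.93 | 0.84 | 0.71 |
| 1 | 1.00 | 1.00 | 1.00 |
| 2 | 1.07 | 1.19 | 1.41 |
| 5 | 1.17 | 1.50 | 2.24 |
| 10 | 1.26 | 1.78 | 3.16 |

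**Step 6: does the plan bound f?** The NLF PK analysis set admits participants "who had at least one quantifiable adjusted nasal lining fluid PK observation post dose will be included in the NLF PK analysis dataset". That removes people with no quantifiable value at all, but leaves their below-LLOQ results in for everyone else, so it does not cap f at a given visit. The serum rule in SAP 4.2.2.3, which reports means as not computed when more than half the values are not quantifiable, is written for serum and is not repeated in 4.2.3.3.

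**Step 7: AZD7442 total.** The sentence equating adjusted with raw AZD7442 does not say whether one or both antibodies must be below LLOQ. If both, it follows from the component rule in the same section. If one is enough, the quantifiable antibody loses its urea correction. Assumed example in LLOQ units, with one antibody at 3, the other below LLOQ and D = 10: the adjusted components under 4.2.3.3 are 3 x 10 = 30 and 1, which sum to 31, but the equal-to-raw sentence gives 3 + 1 = 4. Under 4.2.3.1 the total is (3 + 1) x 10 = 40.

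**The case against.** The best defence is that 4.2.3.3 is the dedicated imputation section and a deliberate override for descriptive work, while 4.2.3.1 only states general formulas. Since the ratio's numerator is the adjusted concentration, a value set to LLOQ under 4.2.3.3 could be carried into the ratio, and the two outputs would then agree. That reading is available, so a reader who infers that the outputs are certain to disagree goes further than the text. It is not the plain reading, however. The component rule in 4.2.3.3 names only concentration summaries, and the substitution in 4.2.3.1 stands directly under the ratio formula. Even if adopted, it leaves the mixed scale in the concentration summaries.

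A reader might also infer that multiplying the tabulated ratio by serum concentration would expose the mismatch. The planned outputs largely do not permit that check. Below-LLOQ component concentrations are listed only as below LLOQ. Medians, extremes and arithmetic means of a ratio times serum would not generally return the adjusted statistic even under one rule. Geometric means would do so only over identical paired samples, which the SAP does not promise.

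Substituting a single value for a censored result is conventional, so plain LLOQ is not wrong in itself. The objection to materiality also stands: G and f in the table are assumptions and say nothing about this trial. The endpoint is exploratory, no hypotheses are tested, the number below LLOQ is reported, and NLF samples are taken only when supplies are available (protocol 8.5.2.3).

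**Conclusion.** The conflict between the two sections is real, and it is minor. A below-LLOQ component has an adjusted value of LLOQ x D in 4.2.3.1 and LLOQ in 4.2.3.3. On the plain reading the first feeds the partition ratio and the second the concentration summaries. The outputs may therefore rest on different values, and the 4.2.3.3 summaries combine urea-adjusted with unadjusted values.

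The difference is exactly D per below-LLOQ sample and G^f on a visit's geometric mean. Both are algebraic results and need no assumption about a common D. Their numerical size in this trial cannot be stated, because D, LLOQ and f are absent from the documents; even the direction depends on whether D is above or below 1.

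The effect is confined to exploratory, descriptive NLF tables and figures. No safety, ADA, serum PK or neutralizing antibody result changes. The AZD7442 sentence is a wording matter: it misleads only on the one-antibody reading, and 4.2.3.4.4 names outputs by antibody without clearly planning a separate adjusted AZD7442 table. The documents do not show which section is the error.

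**What to change.** Reconcile 4.2.3.1 and 4.2.3.3 with one below-LLOQ rule, and state that it applies to the component summaries, the partition ratio and any AZD7442 total. The sponsor should choose between two options:

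- **Adjust after substitution.** Set the raw value to LLOQ, then multiply by that sample's urea ratio, as the 4.2.3.1 formula does. All values are on one scale, but imputed values vary with the sample's urea.
- **Plain LLOQ.** State in both sections that the adjusted value is LLOQ, and use it in the partition ratio as well. Imputed values are constant, but the step in scale at LLOQ remains.

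In either case, define adjusted AZD7442 as the sum of the adjusted components. The sentence setting it equal to raw AZD7442 should be deleted under the first option, and limited to samples with both antibodies below LLOQ under the second.

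The cost is a few lines of SAP text and the matching programming. No new data are needed.

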4.2.2.3 Handling of Dropouts and Missing Data

PK and PD analyses will be based on participants with data available. However, the following imputation methods will be used for descriptive analyses of PK and PD, respectively.

Pharmacokinetics data

Individual concentrations below the LLOQ of the bioanalytical assay will be reported as Not Quantifiable (NQ) in the listings with the LLOQ defined in the footnotes of the relevant tables, figures, and listings (TFLs). Serum concentrations that are NQ or not reported (NR) will be handled as follows for the provision of descriptive statistics:

- Any values reported as NR will be excluded from the summary tables and corresponding figures.
- At a time point where less than or equal to 50% of the concentration values are NQ, all NQ values will be set to the LLOQ, and all descriptive statistics will be calculated accordingly.
- At a time point where more than 50% (but not all) of the values are NQ, the mean, SD, geometric mean, gSD and geometric coefficient of variation (gCV%) will be set to Not Computed (NC). The maximum value will be reported from the individual data, and the minimum and median will be set to NQ.
- If all concentrations are NQ at a time point, no descriptive statistics will be calculated for that time point. The mean, minimum, median, and maximum will be reported as NQ and the gCV% and geometric mean and gSD as NC.
- The number of values below LLOQ ($n < \text{LLOQ}$) will be reported for each time point together with the total number of collected values (n).

- If only two observations are > LLOQ then the minimum and maximum are presented with the other summary statistics as NC.

SARS-CoV-2 Neutralizing Antibodies

The analysis of neutralizing antibody GMT and GMFR will use the following imputation method: a titer value measured below the LLOQ will be imputed to a value that is half of the LLOQ in summaries and analyses but will be listed as reported in the raw data. Titer values measured as above the upper limit of quantification (ULOQ) will be imputed at the ULOQ value.

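### Nasal-fluid values below LLOQ are replaced without the serum cap at 50%, and the SAP gives two different adjusted values for the same unquantifiable sample

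*SAP*

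**What the plan says.** **Serum (SAP 4.2.2.3).** The rule opens: "Serum concentrations that are NQ or not reported (NR) will be handled as follows". It then sets a ceiling. "At a time point where more than 50% (but not all) of the values are NQ", the mean, SD, geometric mean, gSD and gCV% become NC, and the minimum and median become NQ.

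**Nasal fluid, summaries (SAP 4.2.3.3).** "Value of LLOQ will be used for both raw and adjusted AZD8895 and AZD1061 concentrations" in the component summaries, with no ceiling. For the combined product: "Adjusted AZD7442 concentration is same as raw AZD7442 concentration in such cases".

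**Nasal fluid, formulas (SAP 4.2.3.1).** The adjusted concentration is the raw value times the ratio of serum to NLF urea. Despite its name, the Serum:NLF partition ratio has the adjusted nasal value in the numerator and serum in the denominator. The section adds: "When Raw NLF concentration < LLOQ for either AZD8895 or AZD1061, replace it with LLOQ for the calculation".

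**What is reported (SAP 4.2.3.4.4).** The "adjusted NLF concentrations data and serum to NLF partition ratio will be listed and tabulated by mAb component", and both are also plotted. The link to the serum section is: "Same record exclusion criteria as explained in previous section 4.2.2.4.1 will be applied". That imports record exclusions, not the NQ rule of 4.2.2.3.

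**The concern.** Nasal concentration of AZD7442 is a stated exploratory endpoint. The SAP recognises for serum that a mean built mostly from substituted values should not be printed, but does not carry this over to nasal fluid. A visit with nearly all values below LLOQ would still show a geometric mean, a gSD and a plotted point.

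The two nasal rules also disagree. Under 4.2.3.1 an unquantifiable sample has adjusted value LLOQ × urea factor. Under 4.2.3.3 it has LLOQ, while quantifiable samples in the same table are still multiplied by the urea factor. The choice changes the size of the bias and can change its direction. It also carries into the partition ratio, where a fixed nasal value over a falling serum value produces a trend that is not a nasal measurement.

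**Working it through.** The documents state no nasal figure, so there is none to reproduce.

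**Inputs**
- From the documents: serum half-life about 90 days (Protocol 2.2, Phase I, healthy adults); Arm B dosed on Days 1 and 183, Arm A re-dosed on Day 92 (Protocol 1.1); sampling at Days 29, 92 and 183 (Protocol 1.3).
- Assumed: raw NLF values lognormal with log SD *s*; share *p* below LLOQ; median urea factor *D*, independent of the raw value.

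**1. Geometric mean of the adjusted value**

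Let *z* be the standard normal quantile of *p*, φ the normal density, and g(*z*) = *z*·*p* + φ(*z*). Then, relative to the true geometric mean:
- 4.2.3.1 (LLOQ × urea factor): exp(*s*·g)
- 4.2.3.3 (bare LLOQ): exp(*s*·g) × *D*^(−*p*)

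At *p* = 0.80: *z* = 0.8416, φ = 0.2800, g = 0.6733 + 0.2800 = 0.9533.

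| Log SD | 4.2.3.1 | 4.2.3.3, D = 5 | D = 10 | D = 20 |
|---|---|---|---|---|
| 1.0 | 2.59 | 0.72 | 0.41 | 0.24 |
| 1.5 | 4.18 | 1.15 | 0.66 | 0.38 |

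The multipliers *D*^(−0.8) are 0.276, 0.158 and 0.091. At *p* = 0.90, g = 1.3289: 4.2.3.1 gives 3.8 to 7.3, and 4.2.3.3 with *D* = 10 to 20 gives 0.25 to 0.92. For raw values, the gSD at 80% below LLOQ shrinks from 2.7–4.5 to 1.4–1.6.

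**2. Ratio for one participant below LLOQ at two visits**

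The nasal value is fixed, so the ratio moves inversely with serum:
- Day 29 to 183 (Arm B, no dose between): 2^(154/90) = 3.27-fold rise.
- Day 29 to 92 (up to Arm A's next dose): 2^(63/90) = 1.62-fold rise.

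Under 4.2.3.1 the ratio also moves with any change in the urea factor.

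**3. Group geometric mean ratio, Day 29 to 183**

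Let nasal and serum levels fall in parallel, so that the true ratio is constant and should show 1.00 (*s* = 0.8, *D* = 10). Then *z* at Day 183 is *z* at Day 29 + ln(3.27)/0.8. The change is exp(0.8 × change in g) under 4.2.3.1, multiplied by 10^(−change in *p*) under 4.2.3.3.

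| Below LLOQ, Day 29 | Below LLOQ, Day 183 | 4.2.3.1 | 4.2.3.3 |
|---|---|---|---|
| 30% | 83% | 1.99 | 0.58 |
| 50% | 93% | 2.44 | 0.90 |
| 80% | 99% | 3.00 | 1.94 |
| 95% | 99.9% | 3.22 | 2.88 |

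**4. Ratios from quantifiable samples only**

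The mean log excess is *s*·φ(*z*)/(1 − *p*). With *s* = 0.8 to 1.0 and the same serum fall, the ratio still rises 2.4 to 2.5-fold starting at 50% below LLOQ, and about 2.7-fold starting at 80%. At 80% the starting level is overstated 3.1 to 4.1-fold, against 2.1 to 2.6-fold with substitution under 4.2.3.1. Dropping unquantifiable samples is therefore not a remedy.

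**The case against.** Four points on the other side carry weight.

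- **The share is normally visible.** SAP 3.3 calls for n and n < LLOQ with concentration data when applicable, and 4.2.3.3 lists such values as below LLOQ. A reader might infer that unquantifiable data would be hidden, but the text does not support that for concentrations. Neither provision is stated for the ratio or the figures.
- **A participant below LLOQ at every visit is not analysed.** The NLF PK analysis set (SAP 3.2) requires at least one quantifiable adjusted value after dosing. The purely serum-driven ratio therefore arises only between visits that are both below LLOQ. The set does not limit the share below LLOQ at any one visit.
- **The direction is not fixed.** A reader might infer that nasal levels are always inflated towards LLOQ, or that the ratio can only rise. The inflation holds for raw values and under 4.2.3.1. The tabulated value is urea-adjusted, and under 4.2.3.3 both its geometric mean and the group ratio can be too low.
- **Importance is limited.** The endpoint is exploratory and descriptive, no hypothesis is tested, and no document says that most nasal values will be below LLOQ.

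These points limit the size and reach of the problem. They do not supply the missing ceiling or settle the conflict between the two sections.

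**Conclusion.** Two defects rest on the text alone: NLF has no counterpart to the serum rule at 50%, and SAP 4.2.3.1 and 4.2.3.3 define the adjusted value of an unquantifiable sample differently. At visits mostly below LLOQ, the adjusted concentration and the partition ratio would mainly describe the substitution.

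The sizes are illustrative. With 80% below LLOQ and log SD 1.0 to 1.5, the geometric mean is 2.6 to 4.2 times the true value under 4.2.3.1. It is 0.24 to 0.66 of it under 4.2.3.3 with a urea factor of 10 to 20. For a participant below LLOQ at both visits, the ratio rises 3.27-fold from Day 29 to Day 183 in Arm B, apart from urea changes under 4.2.3.1. That figure assumes the healthy-adult half-life applies. Because Arm A is re-dosed at Day 92, the artefact can differ between arms. The documents do not support a claim that the bias always runs one way or that nasal values will in fact be mostly unquantifiable.

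**What to change.** Amend SAP 4.2.3.3, with matching text in 4.2.3.1 and 4.2.3.4.4, before the nasal tables are produced:

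1. Apply the NC/NQ rule of 4.2.2.3 to NLF concentrations when more than 50% at a time point are below LLOQ.
2. At those visits, also set partition-ratio summaries and figure points to NC/NQ, and show n < LLOQ with the ratio. The serum rule covers concentrations only, so the ratio needs its own sentence. Do not summarise quantifiable-only ratios instead, because they select high values.
3. For visits at or below 50%, choose one substitution and give substituted and quantifiable values the same urea correction, including in the AZD7442 sum.

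The cost is a few sentences reusing a rule the SAP already has, with no change to data collection. Some cells will print NC. Some bias remains below the ceiling: at exactly 50% below LLOQ, substitution under 4.2.3.1 still inflates the geometric mean by exp(0.3989·*s*), or 1.49 to 1.82-fold for *s* = 1.0 to 1.5. The SAP already accepts substitution at LLOQ for serum.
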